9.2.3 Reporting Serious Adverse Events After the Protocol-required Reporting Period

After the protocol-required reporting period defined above **or after end of study**, the investigator does not need to actively monitor subjects for serious adverse events. However, if the investigator becomes aware of a serious adverse event after this protocol required reporting period **or after end of study**, the investigator will report the event to Amgen within 24 hours following the investigator's knowledge of the event.

Serious adverse events reported outside of the protocol-required reporting period **or after end of study** will be captured within the safety database as clinical trial cases for the purposes of expedited reporting.

If a site receives a report of a new serious adverse event from a study subject or receives updated data on a previously reported serious adverse event after the

EDC has been taken off-line, then the site can report this information on a paper Serious Adverse Event Report Form (eSAE Contingency Report Form).

9.3 Pregnancy and Lactation Reporting

If a pregnancy occurs in a female subject, or female partner of a male subject, while the subject is taking **evolocumab** report the pregnancy to Amgen as specified below.

In addition to reporting any pregnancies occurring during the study, investigators should monitor for pregnancies that occur after the last dose of evolocumab and for an additional 15 weeks after the end of treatment with evolocumab, report the pregnancy to Amgen as specified below.

The pregnancy should be reported to Amgen **Global Patient Safety** within 24 hours of the investigator's knowledge of the event of a pregnancy. Report a pregnancy on the Pregnancy Notification Worksheet ([Appendix C](#)). **Amgen Global Patient Safety will follow-up with the investigator regarding additional information that may be requested.**

Abnormal pregnancy outcomes (eg, spontaneous abortion, fetal death, stillbirth, congenital anomalies, ectopic pregnancy) are considered serious adverse events.

If a lactation case occurs while the female subject is taking evolocumab, report the lactation case to Amgen as specified below.

In addition to reporting a lactation case during the study, investigators should monitor for lactation cases that occur after the last dose of **evolocumab** through an additional 15 weeks after the end of treatment with **evolocumab**, report the lactation case to Amgen, as specified below.

Any lactation case should be reported to Amgen **Global Patient Safety** within 24 hours of the investigator's knowledge of event. Report a lactation case on the Lactation Notification Worksheet ([Appendix C](#)). **Amgen Global Patient Safety will follow-up with the investigator regarding additional information that may be requested.**

If a male subject's female partner becomes pregnant, the investigator should discuss obtaining information regarding the birth outcome and health of the infant from the pregnant partner.

10. STATISTICAL CONSIDERATIONS

10.1 Study Endpoints, Analysis Sets, and Covariates

10.1.1 Study Endpoints

Co-Primary Endpoints:

- Mean percent change from baseline in LDL-C at weeks 10 and 12, and
- Percent change from baseline in LDL-C at week 12.

Co-Secondary Efficacy Endpoints:

Co-secondary endpoints of the means at weeks 10 and 12 and at week 12 for:

Tier 1

- Change from baseline in LDL-C
- LDL-C response (LDL-C < 70 mg/dL [1.8 mmol/L])
- Percent change from baseline in total cholesterol
- Percent change from baseline in non-HDL-C
- Percent change from baseline in ApoB
- Percent change from baseline in the total cholesterol/HDL-C ratio
- Percent change from baseline in ApoB/ApoA1 ratio

Tier 2

- Percent change from baseline in Lp(a)
- Percent change from baseline in triglycerides
- Percent change from baseline in HDL-C
- Percent change from baseline in VLDL-C

Tertiary Efficacy Endpoints

- Mean percent change from baseline in ApoA1 at weeks 10 and 12
- Percent change from baseline in ApoA1 at week 12

Exploratory Endpoints

- Subject incidence of non-coronary revascularization
- Observed values, change and percent change from baseline at each scheduled visit in each of the following parameters:
 - LDL-C
 - Total cholesterol
 - non-HDL-C
 - ApoB
 - Total cholesterol/HDL-C ratio

- ApoB/ApoA1 ratio
- VLDL-C
- HDL-C
- ApoA1
- Triglycerides
- Lp(a)
- hsCRP at each scheduled assessment
- PCSK9 change from baseline at each scheduled assessment

Safety Endpoints

- Subject incidence of adverse events
- Safety laboratory values at each scheduled visit
- Incidence of anti-evolocumab antibody (binding and neutralizing) formation

Pharmacokinetics Endpoints

- Serum concentration of evolocumab at selected time points

10.1.2 Analysis Sets

Full Analysis Set

The full analysis set (FAS) includes all randomized subjects who received at least 1 dose of IP in the double blind treatment period. This analysis set will be used in both efficacy and safety analyses for the double blind treatment period.

Generally, in efficacy analyses, subjects will be grouped according to their randomized treatment group assignment and by pooled treatment. In safety analyses, subjects will be grouped according to their randomized treatment group assignment with the exception: if a subject receives treatment throughout the study is different than the randomized treatment group assignment, then the subject will be grouped by the actual treatment group.

Completer Analysis Set

The completer analysis set (CAS) includes subjects in the FAS who adhered to the scheduled IP in the double blind treatment period and have observed values for the co-primary endpoints.

Open Label Extension Period Analysis Set

The open label extension period analysis set (OLEAS) includes subjects in the FAS who received at least 1 dose of evolocumab in the open label extension period. This analysis set will be used in both efficacy and safety analyses for the open label extension period.

10.1.3 Covariates and Subgroups

Baseline covariates include, but are not limited to:

- Stratification factors:
 - Screening LDL-C level: < 180 mg/dL [4.7 mmol/L] vs. ≥ 180 mg/dL
 - Baseline statin use: yes vs. no

The following baseline covariates may be used for subgroup or covariate analyses with the subgroups as specified or in their original format:

- Age: < 65 years, ≥ 65 years; < 75 years, ≥ 75 years
- Sex
- LDL-C: < baseline median, ≥ baseline median
- PCSK9 level: < baseline median, ≥ baseline median
- Baseline lipid regulating medications use: yes vs. no

10.2 Sample Size Considerations

The planned sample size for the comparison between evolocumab and ezetimibe is 40 (20 in Q2W and QM each) and 20 subjects (10 in Q2W and QM each), respectively (60 total). The primary analysis will require the 2-sided tests of each co-primary endpoint to be significant at a level of 0.05. From the global phase 3 study 20110116, the treatment effect of evolocumab compared to ezetimibe for reduction from baseline in LDL-C at week 12 is at least 37.6% (32.9%, 42.2%) and for the mean of week 10 and 12, 36.9% (31.6%, 42.3%). Assuming 5% of randomized subjects do not receive any IP and with a common standard deviation (SD) of approximately 20%, this study has at least 93% power to detect a treatment effect of 20% or greater reduction for each of the co-primary endpoints in testing the superiority of evolocumab over ezetimibe, based on a two-sided t-test with significance level 0.05.

As the co-primary endpoints are correlated, there is at least 85% (93% x 93%) power to detect significant treatment effects of the co-primary endpoints. The power calculation is derived using nQuery version 7.01.

10.3 Access to Individual Subject Treatment Assignments by Amgen or Designees

Blinded individuals will not have access to unblinded information until the study is formally unblinded. Unblinding and potentially unblinding information should not be distributed to the study team, investigators or subjects prior to the study being formally unblinded except as specified (eg, [Section 5.2](#) and [Section 9.2.2](#)).

The independent DMC members, and Independent Biostatistical Group (IBG) will have access to treatment assignments and subject level data from the clinical trial database. Amgen staff members who are involved in randomization, biological sample management, and performing PK and anti-evolocumab antibody assay analysis will have treatment assignment information, but will not have access to subject level data from the clinical trial database.

10.4 Planned Analyses

10.4.1 Data Monitoring Committee (DMC)

An external independent DMC has been established to formally review the accumulating data from this and other completed and ongoing studies with evolocumab to ensure there is no avoidable increased risk for harm to subjects. The independent DMC is chaired by an external academic cardiologist who is an expert in lipids and clinical trials. Analyses for the DMC are provided by the Independent Biostatistical Group (IBG), which is external to Amgen. Details are provided in the DMC charter.

10.4.2 Primary Analysis

To evaluate efficacy and safety of 12 weeks of evolocumab compared with ezetimibe **and summarize 12 weeks of data from the open-label extension (weeks 12 to 24)**, the primary analysis will be performed when all the randomized subjects in the study have either completed the scheduled visits up to and including Week **24** or have early terminated from the study. At that time, the database of the study will be cleaned, processed and a snapshot will be taken; the study will also be unblinded.

10.4.3 Final Analysis

The final analysis will be conducted when all enrolled subjects have either completed the scheduled visits or have early terminated from the study. At that time, the database of study will be cleaned, processed and a snapshot will be taken. The long-term safety and efficacy of evolocumab will be assessed.

10.5 Planned Methods of Analysis

10.5.1 General Considerations

Based on the snapshot for the primary analysis, efficacy and safety analyses will be performed on the FAS. Unless otherwise specified, the FAS will be the default analysis set for the primary analysis and data will be summarized by randomized treatment group assignment and by pooled frequency for evolocumab and pooled ezetimibe. The **treatment effect** of evolocumab **compared** to ezetimibe will be **evaluated** for all efficacy endpoints **through the Week 12 visit. In addition, descriptive analyses from the open-label extension (weeks 12 to 24) will be performed on OLEAS.**

Based on the snapshot for the final analysis, long-term efficacy and safety analyses will be performed on OLEAS and the analyses will be descriptive.

[figure not shown]
Subject disposition, demographics, baseline characteristics, and exposure to IP will be summarized.

Summary statistics for continuous variables will include the number of subjects, mean, median, Q1, Q3, standard deviation or standard error, minimum, and maximum. For categorical variables, the frequency and percentage will be given.

Missing data will not be imputed for safety endpoints.

Multiplicity Adjustment Method

Methods of adjusting for multiplicity due to multiple endpoints (co-primary and co-secondary efficacy endpoints) in order to preserve the familywise error rate at 0.05 are described in the diagram below.

Testing of each co-endpoint pair for the pooled evolocumab vs. pooled ezetimibe analysis will result in a single p-value, and for co-secondary endpoints these p-values will then be used in the Hochberg procedure. The following test procedure will be used to preserve the familywise error rate for the co-primary and co-secondary endpoints:

1. If the treatment effect from the primary analysis of the co-primary endpoints are both significant at a significance level of 0.05, statistical testing of the tier 1 co-secondary efficacy endpoints will follow the Hochberg procedure at a significance level of 0.005 (Hochberg, 1988).
2. If all tier 1 co-secondary efficacy endpoints are significant, the tier 2 co-secondary efficacy endpoints will be tested using the Hochberg procedure at a significance level of 0.05.
3. If not all tier 1 co-secondary efficacy endpoints are significant, the tier 2 co-secondary efficacy endpoints will be tested using the Hochberg procedure at a significance level of 0.045 (Wiens, 2003).

Unless specified otherwise, all other hypothesis testing will be 2-sided with a significance level of 0.05.

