1.2 Secondary

- To evaluate the safety and tolerability of **subcutaneous (SC)** evolocumab, compared with ezetimibe, in hypercholesterolemic subjects unable to tolerate an effective dose of a statin
- To assess the effects of 12 weeks of evolocumab, compared with ezetimibe, on change from baseline in LDL-C, and percent change from baseline in non high density lipoprotein cholesterol (non HDL-C), total cholesterol (TC), apolipoprotein B (ApoB), total cholesterol/HDL-C ratio, ApoB/Apolipoprotein A1 (ApoA1) ratio, lipoprotein(a) [Lp(a)], triglycerides, very low-density lipoprotein cholesterol (VLDL-C), and HDL-C in hypercholesterolemic subjects unable to tolerate an effective dose of a statin
- To assess the effects of 12 weeks SC evolocumab, compared with ezetimibe, on percent of subjects attaining LDL-C < 70 mg/dL (1.8 mmol/L) in hypercholesterolemic subjects unable to tolerate an effective dose of a statin

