10.5 Efficacy Analyses

The following table summarizes the key efficacy analyses that will be conducted.

Table 3. Key Efficacy Analyses Summary

Endpoint	Statistical Analysis Method	P-values from the Statistical Tests	Hierarchical Testing Procedure as Specified in the Multiplicity Adjustment Method Diagram
			Testing of Pooled EvomabTreatment Effect vs. Ezetimibe
Co-Primary Endpoints			

 Mean percent change from baseline at weeks 10 and 12 in LDL-C Percent change from baseline at week 12 in LDL-C 	Repeated measures model	P1 = Maximum of the two p-values for the co-endpoint pair from the primary analysis in FAS	P1 compare to $\alpha = 0.05$
Co-Secondary Endpoints (Tier 1)			

 Mean LDL response (achievement of LDL-C < 70 mg/dL) at weeks 10 and 12 LDL response at week 12 	Cochran Mantel-Haenszel (CMH) test	P2a = Maximum of the two p-values for the co-endpoint pair in FAS	
If P1 < 0.05, \rightarrow P2a and all P2b's will be tested through Hochberg method with $\alpha = 0.005$
 
Else (ie, co-primary endpoint in FAS is not significant) \rightarrow No further testing.

 Mean change from baseline at weeks 10 and 12 in LDL-C Change from baseline at week 12 in LDL-C and Mean percent change from baseline at weeks 10 and 12 Percent change from baseline at week 12 in each of the following lipid parameter: total cholesterol, non-HDL-C, ApoB, total cholesterol/HDL-C ratio, ApoB/ApoA1 ratio 	Repeated measures model	
For each lipid parameter, P2b = Maximum of the two p-values for each co-endpoint pair in FAS
	
Co-Secondary Endpoints (Tier 2)			

 Mean percent change from baseline at weeks 10 and 12 Percent change from baseline at week 12 in each of the following lipid parameters: Lp(a), triglycerides, HDL-C, and VLDL-C 	Repeated measures model	
For each lipid parameter, P2c = Union-intersection test p-value from the two contrasts of each co-endpoint pair in FAS
	
If P2a and all P2b's are significant through Hochberg method, \rightarrow P2c will be tested through Hochberg method with $\alpha = 0.05$.
 
Else (ie, not all tier 1 co-endpoints in FAS are significant), \rightarrow P2c will be tested through Hochberg method with $\alpha = 0.045$.

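### Alpha spent on Tier 2 never returns to Tier 1, so LDL-C response stays at 0.005 even when every Tier 2 pair is rejected

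*Protocol*

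**What the plan says.** Protocol 10.5.1 and SAP 10.1 set out a scheme "in order to preserve the familywise error rate at 0.05". Both co-primary endpoints must first be significant at 0.05. Then "statistical testing of the tier 1 co-secondary efficacy endpoints will follow the Hochberg procedure at a significance level of 0.005". If all of Tier 1 is significant, Tier 2 gets 0.05. If not, "the tier 2 co-secondary efficacy endpoints will be tested using the Hochberg procedure at a significance level of 0.045". SAP Table 3 repeats this: "P2a and all P2b's will be tested through Hochberg method with" a level of 0.005.

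Tier 1 holds seven co-endpoint pairs. Six are continuous lipid measures. The seventh is LDL-C below 70 mg/dL, which also has its own secondary objective in protocol 1.2: the effect "on percent of subjects attaining LDL-C < 70 mg/dL (1.8 mmol/L) in hypercholesterolemic subjects". SAP 10.5.2 tests it with a CMH test. SAP Table 3 takes the larger of the two p-values in the pair, and SAP 6.3 counts a missing value as non-response. Tier 2 holds four pairs: Lp(a), triglycerides, HDL-C and VLDL-C.

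Neither document gives a reason for the 0.005/0.045 split, an expected responder rate, a mean baseline LDL-C, or a power figure for any secondary endpoint.

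**The concern.** The scheme passes alpha from Tier 1 to Tier 2 but not back. When all four Tier 2 pairs are rejected at 0.045, that 0.045 could be used again for Tier 1 at no cost in error. The plan leaves it unused, so Tier 1 still carries only 0.005 of the 0.05.

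This matters most for LDL-C response. It is a dichotomised endpoint in a small trial and is likely to have the largest Tier 1 p-value. If it does, Hochberg compares it with 0.005 itself, or with 0.0025 or less if another pair also fails. The trial could reject every Tier 2 pair, see a response p-value of 0.01 to 0.04, and still have to declare this objective not met.

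**Working it through.** **The plan's own figure.** Protocol 10.2 has 60 randomized, 40 versus 20, with 5% never dosed: 60 x 0.95 = 57, or 38 versus 19. It states that "The primary analysis will require the 2-sided tests of each co-primary endpoint to be significant at a level of 0.05". For a 20-point difference and SD 20, the noncentrality is 20 / (20 x sqrt(1/38 + 1/19)) = 20 / 5.62 = 3.56. Two-sided t-test power at 0.05 is 93.8%, which reproduces the stated 93%.

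**Continuous LDL-C at 0.005** (same formula):

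| Difference (points) | Power at 0.005 |
|---|---|
| 37.6 | 99.99% |
| 36.9 | 99.98% |
| 31.6 (lower limit in protocol 10.2) | 99.5% |
| 20 (design effect) | 73% |

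At the planning effect, 0.005 is no obstacle for LDL-C as a continuous measure.

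**Response endpoint, by counts.** Take an unstratified CMH test with x responders of 38 on evolocumab and 0 of 19 on ezetimibe. Chi-square = (x/3)^2 / [38 x 19 x x(57 - x) / (57^2 x 56)].
- x = 7 (18%): 5.444 / 1.389 = 3.92, p = 0.048
- x = 12 (32%): 16 / 2.143 = 7.47, p = 0.0063
- x = 13 (34%): 18.78 / 2.270 = 8.27, p = 0.0040

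So 7 responders are enough at 0.05, and 13 are needed at 0.005.

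**Response endpoint, by power.** Inputs from the documents: ezetimibe -18.1% (protocol 2.3), evolocumab -18.1 - 37.6 = -55.7%, SD 20, 38 versus 19, and a floor of 100 mg/dL, the lowest entry threshold in criterion 103. Assumed, because the documents do not give them: mean baseline LDL-C, baseline SD 35 mg/dL and visit correlation 0.7. The test is a CMH test stratified at 180 mg/dL, taking the larger p-value of the pair. The ranges below are over repeat simulations.

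| Mean baseline (mg/dL) | Power at 0.005 | Power at 0.045 | p between 0.005 and 0.05 |
|---|---|---|---|
| 140 | 0.89-0.90 | 0.98-0.99 | 0.09-0.10 |
| 160 | 0.79-0.81 | 0.97-0.98 | about 0.16 |
| 180 | 0.62-0.65 | 0.94-0.95 | about 0.33 |
| 200 | 0.36-0.37 | 0.87-0.89 | 0.52-0.53 |

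Adding the last column to the first gives power at 0.05 of about 88-99%. Baseline dominates because a 55.7% fall reaches 70 mg/dL from 70 / (1 - 0.557) = 158 mg/dL. With SD 15 in place of 20, power at 0.005 runs from 0.98 down to 0.27.

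**Freely chosen responder rates.** The normal approximation for 30% versus 5% has a pooled rate of (38 x 0.30 + 19 x 0.05) / 57 = 0.217. The standard errors are 0.1158 under the null and 0.0896 under the alternative. Then z = (0.25 - 2.807 x 0.1158) / 0.0896 = -0.84, so power is 20%. For 60% versus 2% it is 99%.

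**Validity of a return step.** Hochberg at 0.045 rejects all four Tier 2 pairs exactly when the largest Tier 2 p-value is at most 0.045. Every intersection containing a Tier 2 hypothesis is then already rejected. Only intersections made up of Tier 1 hypotheses remain, and each may be tested at 0.05. Simulated familywise error is about 0.05 with or without the step. The dependence condition is the one Hochberg already needs in the written plan.

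**Size of the gain.** If the other Tier 1 pairs pass, the gain is P(0.005 < response p <= 0.05) x P(all Tier 2 pairs rejected), assuming independence. The first factor is about 0.10-0.53. The second cannot be computed, because the documents give no between-arm effects for Tier 2. Taking 0.10 to 0.60 as an assumed range: 0.10 x 0.10 = 0.01 and 0.53 x 0.60 = 0.32.

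**The case against.** **The plan makes no error.** 0.005 + 0.045 = 0.05, the scheme follows a cited fallback method, and both documents apply it consistently. This stands: a reader might infer that error control is at fault, and it is not. What is lost is power.

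**The power range is not a property of the plan.** This also stands. It rests on an assumed baseline LDL-C. That response has the largest Tier 1 p-value is likely but not shown, because no effects are given for the non-LDL lipids. At the 20-point design effect, even continuous LDL-C has only 73% power at 0.005.

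**The weights look the wrong way round.** A reader might infer that Tier 1 should have 0.045 and Tier 2 0.005. The documents do not support that. The present split guarantees at least 0.045 to four other named secondary endpoints whatever Tier 1 does. At the 20-point design effect, under the same model, the response pair passes at 0.045 in only about 3-36% of trials. Swapped weights would then leave Tier 2 at 0.005 in at least 64-97% of trials. The swap is a trade-off, not an improvement.

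**It is too late.** SAP 10.1 describes a completed primary analysis with a data cut-off of 02 November 2017 and says the blinded-period analyses will not be repeated. Protocol 10.4.2 places unblinding at that analysis. This limits when the rule can change, but it does not alter the finding about the design.

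**Conclusion.** The point holds as a missed free improvement. The scheme controls familywise error but leaves 0.045 unused for Tier 1 whenever all of Tier 2 is rejected.

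LDL-C response bears most of the loss. Under the stated assumptions its pair has about 36-89% power at 0.005, against about 88-99% at 0.05. Across other plausible responder rates, power at 0.005 runs from about 20% to 99%, so no single figure should be quoted without its conditions.

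The benefit of returning the alpha is about 1-32 percentage points, given independence and joint Tier 2 power of 10-60%. It is zero if any Tier 2 pair misses 0.045.

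**What to change.** In protocol 10.5.1, SAP 10.1 (text and diagram) and SAP Table 3, keep the 0.005/0.045 split and add a fourth step: if not all Tier 1 pairs are significant at 0.005, and all Tier 2 pairs are rejected by Hochberg at 0.045, retest Tier 1 by Hochberg at the full 0.05.

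The cost is wording only, with no change to sample size, data collection or the Tier 2 tests. The step can only add rejections.

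It must be in place before unblinding. If unblinding has taken place, leave the written rule as it is. Report the response difference with its confidence interval, and say that a p-value between 0.005 and 0.05 misses significance because of the alpha allocation and is not evidence of no difference.

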10.5.2 Primary Efficacy Endpoint

Primary Analysis

To assess the co-primary endpoints of the mean percent change from baseline at weeks 10 and 12 and the percent change from baseline at week 12 in LDL-C, a repeated measures linear effects model will be used to compare the efficacy of evolocumab (pooled Q2W and QM) with pooled ezetimibe. The repeated measures model will include terms of treatment group, stratification factor of screening LDL-C level, scheduled visit, and the interaction of treatment group with scheduled visit. Missing values will not be imputed when the repeated measures linear effects model is used.

Sensitivity Analysis

To evaluate the robustness of the primary analysis results, sensitivity analyses will be performed as follows:

- The primary analysis will be repeated using the CAS
- Non-parametric analyses ([Quade, 1979](#))

Additional Analyses

The co-primary endpoints will also be assessed within each dose frequency using dose frequency matched control (ie, evolocumab Q2W SC plus placebo PO QD vs. ezetimibe QD plus placebo Q2W SC; evolocumab QM SC **plus placebo PO QD** vs. ezetimibe QD plus placebo QM SC) and pooled ezetimibe (ie, evolocumab Q2W vs. pooled ezetimibe; evolocumab QM vs. pooled ezetimibe)

In addition, the difference between the evolocumab Q2W and evolocumab QM groups will be estimated.

